PROTOCOL

SU017

A 3 Years Naturalistic Cohort Survey Of Altis® Single Incision Sling System For Female Stress Urinary Incontinence

A post-marketing and multicenter prospective observational cohort study in subjects with female stress urinary incontinence

Date of edition: 26 June 2014

Final Version 1.2

This confidential document is the property of Coloplast Manufacturing France SAS
No unpublished information contained herein may be
disclosed without written approval of Coloplast.

> SYNOPSIS OF THE PROTOCOL

TITLE	
A 3 Years Naturalistic Cohort Survey Of Altis® Single Incision Sling System For Female Stress Urinary Incontinence
 
A post-marketing and multicenter prospective observational cohort study in subjects with female stress urinary incontinence

SPONSOR	
Coloplast Manufacturing France SAS. [name]

DEVICE	
Altis Single Incision Sling System

STUDY TYPE	
Post-market and prospective observational cohort study of subjects implanted with the Altis SIS for female stress urinary incontinence

OBJECTIVES	
Main study objective
 
To monitor the use of Altis Single Incision Sling in a real world population.
 
To assess the clinical effectiveness (defined by the treatment success rate) and to monitor safety of Altis SIS at 12 months post device implantation in women with stress urinary incontinence.
 
Success will be regarded as optimal if the PGI-I score is rated as very much or much or a little improved and no severe/serious event has been reported.
 
Secondary objectives.
 
To assess the clinical effectiveness of Altis SIS over the 3 years post device implantation follow up in real subject population
 
To explore pre-surgery prognosis factors of effectiveness and failure
 
To explore impact of Altis SIS on quality of life
 
To explore impact of Altis on sexual life
 
To document emergent device-related adverse events and safety over the 3 years post device implantation

POPULATION	
Target Subject Population
 
All subjects meeting selection criteria will be invited to participate in the registry. Participating sites are required to do their best efforts to document in the registry all enrolled subjects including those with early revision of the sling for any reason.

Inclusion criteria

1. Female gender
2. At least 18 years of age.
3. Subject implanted with Altis Single Incision Sling System in the participating center, to manage Urinary Incontinence according to Urologist's diagnosis
4. Subject having received written and oral information about study objectives and having accepted that anonymous data issued from his medical dossier will be used for research purposes and will be analyzed by using computer systems. According to national regulations, a written consent to participate may be required.

Non-inclusion criteria

1. Subject who refuses to be included in the survey or that their medical data will be used for research purposes.
2. Indication for Altis Single Incision Sling System implantation is not for the treatment of female UI.
3. Subject already enrolled in any investigational clinical trial of any treatment (drug or device).

Study Sample Size

The total number of subjects enrolled is not limited. However, a minimum of 150 subjects with 12-month available data will be collected. Taking into account a global attrition rate of 20%, 180 patients are targeted for enrolment.

CENTERS

The participating centers will include sites from at least 4 countries across Europe. The study may include sites from France, Germany, Italy and Spain but the number of countries is not limited to these countries.

Around 40 surgeons (5 cases by surgeons) are expected internationally but the number of centres that will be involved in the study is not limited.

STUDY DESIGN

This project will be launched after the first introduction of Altis in Europe. This study is a multicenter prospective, non-interventional (i.e. naturalistic) Post-Marketing cohort follow-up of women with urinary incontinence implanted with Altis Single Incision Sling System. Patients will be recruited by specialised surgeons (urologists, gynaecologists or uro-gynaecologists) who are experienced to the implantation of Altis. They will be followed for 12 months in routine real world clinical practice except for administration of subject questionnaire(s). Routine visits will be performed approximately at baseline (peri-operative period), between 1 and 3 months (immediate post-operative period) and 12 months. An annual follow-up, each year during 2 additional years will also performed via postal questionnaires.

DATA COLLECTION

Clinical data will be collected at baseline (preoperative and implantation), and post-operatively at each visits usually scheduled by the

surgeons. The data will be captured in an electronic data capture system (EDC).

The Data Collection Schedule below provides an outline of the desired types of clinical and subject data expected to be collected at each visit.

None of these exams are mandatory. If they are performed results will -be collected in the EDC.

	Baseline	Operative period	First Immediate postoperative visit (2 Months \pm 1 Mo) ¹	12 Months visit (1 year \pm 2 Mo) ¹	Yearly follow-up (until 3 years)
Informed consent obtained	X				
Demographic information, urogynecologic history	X				
Body Mass Index	X			X	X
Urodynamics/Uroflowmetry (history)	X				
Urethral mobility & Prolapse anatomy	X				
Physician –rated assessments					
Stress urinary & overactive bladder symptoms	X		X	X	X
Cough stress test	X		X	X	X ²
Post void residual urine volume	X	X	X	X ³	
Adverse Event assessment		X	X	X	X
Patient-reported outcomes					
Number of pad/day	X		X	X	X
ICIQ-UI SF & I-QOL & PISQ12	X		X	X	X
PGI-I			X	X	X
Subject satisfaction			X	X	X

1 windows are given for information

2 not requested if data are obtained only by mailed questionnaires

3 not requested if the previous value is normal

## **1. MAIN OBJECTIVES OF STUDY AND STATISTICAL ANALYSIS:**

Coloplast's Altis Single Incision Sling (SLIS) System is a minimally invasive system intended for the treatment of female stress urinary incontinence (SUI) resulting from urethral hypermobility and/or intrinsic sphincter deficiency in women.

To meet the requirements of the AFNOR standard, an observational study has been organized to prospectively collect short and mid-term data in the treatment of the female SUI with Altis SIS in the real world. Indeed, observational studies are essential to understand real world use and compliance patterns, estimate effectiveness, and to adequately evaluate risk management programs.

The primary objective is assessment of clinical effectiveness defined by success that is a composite criterion including the patient global impression of improvement (PGI; very much better, much better, little better) and the absence of serious/severe related adverse event (AE), one year after implantation definition.

The secondary objectives of the study are:

- Clinical effectiveness of Altis SIS over the 3 years of follow-up
- Comparison between pre and post inclusion for other outcomes:
  - Objective: cough stress test, uro-flowmetry exams: post-void residual volume and peak urine flow rate, weights of urinary protection.
  - Subjective: number of pads used, exploration of impact of Altis SIS on quality of life via PGI-I, I-QOL or ICIQ-UI-SF questionnaires, patient's satisfaction, and exploration of impact of Altis SIS on sexual life via PISQ-12 questionnaire.
- Documentation of emergent device-related A.E. and safety over the 3 years post implantation
- To explore the pre-surgery prognosis factors associated of treatment success.

## **2. SUMMARY OF STUDY DESIGN FEATURES:**

### **2.1 Study design:**

This study is a multicenter prospective, observational, post-market cohort study of women with urinary incontinence implanted with Altis Single Incision Sling System. Patients will be recruited by specialized surgeons who are trained to the implantation of Altis. They will be followed for 12 months in routine clinical practice. Data will be collected by questionnaires through an electronic

data capture system during routine visits occurring approximately at baseline, between 1 and 3 months (first follow-up visit) and 12 months. An annual follow-up, each year during 2 additional years will also be performed during a visit at the site or via postal questionnaire at surgeon's discretion or according to his current practice. The objective during these additional follow-ups is to obtain completed patient's self-questionnaires.

## 2.2 Sample size:

Effectiveness of female SUIs managed with sling implantation is not accurately defined and large range of success of the procedure is reported.

Furthermore, definition of success is not standardized and comparison across studies and systems is not feasible due to different used endpoint criteria.

Accordingly if  $p$  is the % of success as defined in this protocol, the product  $p*(1-p)$  should be maximized. According to the interim results of an US study, the PGI score at 1 year is 89.3 %.

So this hypothesis of a 89 % rate could be chosen. Therefore, the minimal sample size to be included to detect this prevalence with a 5 % precision is given as following:

$$n = z^2 p(1-p) / d^2.$$

Precision ( $d$ ) = 5 %      prevalence ( $p$ ) = 89 %      estimated sample size  $n = 150$

The total number of subjects enrolled is not limited. However, a minimum of 150 subjects with 12-month available data will be collected. Taking into account a global attrition rate of 20%, 180 patients are targeted for enrolment.

When 150 subjects will have reached a minimal 12-month follow-up duration and all cases are judged exploitable, Sponsor will take the decision to stop or to continue the current recruitment.

Consequently, the centers have been encouraged to keep on enrolling patients after the first 180 patients defining an open-ended recruitment. Approximately 600 patients have been finally included.

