### 4.1 Primary endpoint:

As defined in protocol:

Treatment success defined by PGI as a little, much better and very better improved and absence of serious or severe related Adverse Event one year after implantation.

Table 1: Definition of treatment success

Patient Global Improvement (PGI-I)	Safety	
	No severe or serious related adverse event reported	At least one severe or serious adverse event reported
Very much better	success	failure
Much better	success	failure
Little better	Success	failure
No change	failure	failure
Little worse	failure	failure
Much worse	failure	failure
Very much worse	failure	failure

As recommended and defined by Scientific Committee /SC:

- Treatment success defined by PGI as much better and very better improved and absence of any serious neither severe nor  $\geq$  grade 3 of Clavien-Dindo classification related Adverse Event one year after implantation.

4.2 Secondary endpoints:

As defined in protocol:

- ✓ Treatment success defined by PGI as a little, much better and very better improved and absence of serious or severe related Adverse Event at first follow-up visit, 2 years and 3 years after implantation.
- ✓ PGI as a little, much better and very better improved at first follow-up visit, 1 year, 2 years and 3 years after implantation.

As recommended and defined by Scientific Committee /SC:

- ✓ Treatment success defined by PGI as much better and very better improved and absence of any serious neither severe nor  $\geq$  grade 3 of Clavien-Dindo classification related Adverse Event at first follow-up visit, 2 years and 3 years after implantation.

- ✓ PGI as much better and very better improved at first follow-up visit, 1 year, 2 years and 3 years after implantation.
- ✓ Treatment success defined by PGI as much better and very better improved, and absence of serious related Adverse Event at first follow-up visit, 1 year, 2 years and 3 years after implantation.
- ✓ Treatment success defined by PGI as much better and very better improved, and absence of  $\geq$  Grade 3 Clavien-Dindo classification related Adverse Event at first follow-up visit, 1 year, 2 years and 3 years after implantation.
- ✓ PGI as much better and very better improved at first follow-up visit, 1 year, 2 years and 3 years after implantation.

Objective exams at baseline, first follow-up visit, one year, two years, three years after implantation:

- ✓ cough stress test,
- ✓ number of pads/day,
- ✓ post-void residual volume,
- ✓ maximum urinary flow rate,

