## **8. CHARACTERISTICS OF STATISTICAL ANALYSES:**

Descriptive statistics for continuous variables will be presented with  $N$ , *Mean*, *SD (standard deviation)*, *Median*, *Q1-Q3 (first and third quartile)*, where  $N$  denotes the number of subjects contributing with non-missing data.

For discrete variables, descriptive statistics will be presented with  $N$  and *percentage* of the number of subjects contributing with non-missing data in the various categories of the variable; the number of missing data will be presented but will not be taken into account in the percentage.

All statistical tests will be carried out as two-sided on a 5% level of significance. All confidence intervals will be 95% intervals.

Comparison between pre and post-operative endpoints for paired proportions will be done by a McNemar's test for binary variables.

Comparison between pre and post-operative endpoints for continuous variables will be done by a paired t-test if they are normally distributed. In case of absence of normality, the alternative is to use Wilcoxon's signed-rank test.

For both continuous or binary variables, the null hypothesis is "no difference between pre and post implantation" against the general alternative of "difference between pre and post implantation".

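### The enrolment target of 180 yields 144 evaluable women at the stated 20% attrition, not the required 150, and the 89% input is a PGI-only rate used for a composite endpoint; the effect on precision is small

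*SAP*

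**What the plan says.** SAP 2.2 sizes the study by the precision of one proportion, n = z²p(1−p)/d². It seeks "the minimal sample size to be included to detect this prevalence with a 5 % precision" and obtains n = 150 with p = 89% and d = 5%. It says that p "is the % of success as defined in this protocol" and that the product p(1−p) ought to be as large as possible. The value used comes from elsewhere: "According to the interim results of an US study, the PGI score at 1 year is 89.3" per cent, followed by "So this hypothesis of a 89 % rate could be chosen".

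The section sets 150 women with 12-month data as a minimum, places no upper limit on enrolment, and adds: "Taking into account a global attrition rate of 20%, 180 patients are targeted for enrolment". The Protocol synopsis, under study sample size, carries the same 150, 20% and 180. SAP 2.2 closes by reporting that "Approximately 600 patients have been finally included".

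The primary endpoint in SAP 4.1 is a composite: "Treatment success defined by PGI as a little, much better and very better improved and absence of serious or severe related Adverse Event one year". SAP 4.1 and 9.2 add a second primary definition from the Scientific Committee. It no longer counts the little-better category as success and also counts related events of Clavien-Dindo grade 3 or higher as failures.

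**The concern.** Three parts of the justification do not fit together.

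- **Attrition.** The target looks like 150 raised by 20%. Allowing for a 20% loss means dividing by 0.80.
- **Input.** The 89% describes PGI alone, while the quantity to be estimated is PGI improvement together with freedom from certain related adverse events. The section itself says that success definitions differ too much between studies to be compared, and then borrows a rate from one.
- **Conservatism.** Maximising p(1−p) means p = 50%. Using 89% does the opposite.

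At stake is whether the sample-size paragraph can be carried into the final report. As written, it fails a simple multiplication, and its precision claim belongs to neither primary definition. The only precision it states is for 150 women, although about four times as many were included.

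**Working it through.** **Inputs.** From SAP 2.2: p = 0.89, d = 0.05, minimum 150 evaluable, attrition 20%, target 180, about 600 included. SAP 2.2 does not state z; I take 1.96 because SAP 8 says "All confidence intervals will be 95% intervals".

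**1. The plan's 150.** 1.96² × 0.89 × 0.11 / 0.05² = 150.4. The 150 reproduces; whether to write 150 or 151 is a matter of rounding.

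**2. The plan's 180.**
- Correct inflation: 150 / (1 − 0.20) = 187.5, so 188.
- The stated figure: 150 × 1.20 = 180. Of the two, only this gives 180.
- Yield of 180 at 20% loss: 180 × 0.80 = 144, six short of 150.
- Loss at which 180 yields 150: 1 − 150/180 = 16.7%.

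**3. Cost of the slip.** Half-width = 1.96 × √(p(1−p)/n). At p = 0.89 it is 5.01 points for n = 150 and 5.11 for n = 144, a difference of 0.10 point.

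**4. The maximisation sentence.** At p = 0.50: 1.96² × 0.25 / 0.05² = 384.1, so 385 evaluable women against the 150 used.

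**5. PGI rate against composite rate.** A woman who meets the composite also meets its PGI part, so on the same PGI categories and in the same women the composite rate cannot exceed the PGI rate. A woman who meets the Scientific Committee definition also meets the protocol definition, so the committee rate cannot exceed the protocol rate. The documents give no composite or related-event rate. The rates below 89% in this table are assumptions.

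| Success rate | Evaluable n for ±5 points | Half-width, n = 144 | n = 150 | n = 480 |
|---|---|---|---|---|
| 89% | 151 | 5.11 | 5.01 | 2.80 |
| 87% | 174 | 5.49 | 5.38 | 3.01 |
| 85% | 196 | 5.83 | 5.71 | 3.19 |
| 80% | 246 | 6.53 | 6.40 | 3.58 |
| 50% | 385 | 8.17 | 8.00 | 4.47 |

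**6. Actual enrolment.** 600 × 0.80 = 480 evaluable, if the 20% applies to 12-month data. The half-width is then at most 4.47 points, reached at p = 0.50. Precision within 5 points at any rate needs 385 evaluable, so it survives a loss of up to 1 − 385/600 = 35.8%.

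**The case against.** The strongest reply is that events have overtaken the paragraph. The 150 was a minimum to be collected, not an expected yield. Enrolment was not capped, and the decision to stop or continue recruitment was to be taken once 150 women had reached 12 months with usable data. A wrong inflation factor could not by itself have left the study with 144. Recruitment has ended with about 600. All of this stands, and it limits the consequence.

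A reader might infer that the study does not deliver its 5-point precision. The documents do not support that: steps 3 and 6 show a loss of 0.10 point at the planned size and a comfortable margin at the actual size.

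A reader might also infer that the composite rate must lie below 89%, so that 150 was certainly too few. That is not established. SAP 2.2 does not say which PGI categories the 89.3% counts. If it counts only the two best categories, the protocol composite, which also accepts a little better, could equal or exceed it. The ordering in step 5 holds only for the same categories in the same women, and the 85% and 80% rows are illustrations.

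The 20% is called global and is not tied to 12 months, while follow-up runs to 3 years. A 12-month loss of 16.7% or less would make 180 sufficient. But the sentence directly follows the 12-month minimum in both documents, and nothing there gives a separate 12-month rate, so the plain reading gives 144.

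Finally, 151 and 189 in place of 150 and 188 is rounding. The cited 89.3% itself gives 146.8.

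**Conclusion.** The point holds as a wrong stated figure and a mismatched precision input, not as a failure of the study's precision. On the plan's own numbers, 180 enrolled gives 144 evaluable; 188 are needed at 20% loss. The 89% is a PGI-only rate with unstated categories, used where the section calls for composite success. The maximisation sentence contradicts the value chosen.

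The attrition slip costs 0.10 point at 89%. The cost of using a PGI rate for the composite cannot be computed from the documents. With about 480 evaluable women the half-width stays under 5 points at any success rate. That rests on about 600 included and a loss no greater than roughly 36%. The SAP gives no expected number of evaluable women. This matters because SAP 7 leaves missing endpoint data missing and SAP 8 bases percentages on non-missing data.

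**What to change.** Amend SAP 2.2 as follows.

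- State that the planned target of 180 corresponds to 16.7% attrition, that 188 would be needed at 20%, and that the Protocol synopsis carries the same figure. This corrects the record without rewriting a past target in one document only.
- Remove the sentence on maximising p(1−p), or reconcile it with the 89%.
- Label the 89% as a PGI-only rate from another study and, if known, say which PGI categories it counts.
- Replace the 5% precision statement with the expected 95% half-width at actual enrolment for both primary composite definitions. With 480 evaluable women this would be 2.8 points at 89%, 3.2 at 85% and 3.6 at 80% (assumed rates), and at most 4.5 at any rate. Update the 480 once the number with 12-month data is known.

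The cost is one paragraph of SAP text. No further enrolment is needed, and no analysis changes.

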## 2.3 Randomization: not applicable

As it is a non-interventional study, there is no randomization.

## 2.4 Study population:

This project involved 4 countries: France, Germany, Italy and Spain and surgeons used Altis in their current practice. Experience in Altis implantation may vary between investigators sites.

The study population will consist of patients meeting all of the inclusion criteria and none of the exclusion criteria.

Inclusion criteria are the following:

- Female gender
- At least 18 years of age
- Subject implanted with Altis Single Incision Sling System in the participating center, to manage urinary incontinence according to urologist's diagnosis
- Subject's having received written and oral information about study objectives and having accepted that anonymous data issued from his medical dossier will be used for research purposes and will be analyzed by using computer systems. According to national regulations, a written consent to participate may be required.

Exclusion criteria are the following:

- Subject who refuses to be included in the survey or that their medical data will be used for research purposes
- Indication for Altis Single Incision Sling System implantation is not for the treatment of female UI.
- Subject already enrolled in any investigational clinical trial of any treatment (drug or device).

Subject withdrawal:

Patients will be totally free to withdraw from the study at any time.

## 2.5 Study assessments:

Assessments were based on both physician and patient reported outcomes (PRO). These PRO can be obtained by validated self-questionnaires given at the medical center during a patient's visit or sent by mail.

## 2.6 Study product:

Altis Single Incision Sling (SIS) System is a CE-marked since 2012 and already marketed implantable device. All the patients included in this study had a surgery but a few of them have not been finally implanted with Altis (implantation failure) and another device may have been implanted (results from interim analysis).

### 3. VARIABLES TO BE SUBJECTED TO STATISTICAL ANALYSES:

#### 3.1 At baseline:

- *Subject's demographics & Medical History:*
  - Age (+ sub groups: <65 and  $\geq 65$  year-old)
  - BMI (+ sub groups: lower-normal/over/obesity) (< 25/ 25-29,99 /  $\geq 30$ )
  - Lifestyle (active, sedentary)
  - Smoking status
  - Comorbidities/medical/surgery/uro-gynecological history including Pelvic organ prolapse / hysterectomy / SUI
  - Menopausal status
  - Category of urinary incontinence (SUI, MUI, UUI, other UI)
  - Duration and cause of stress component (+ subgroups: < 5 years and  $\geq 5$  years)
  - Previous treatments of UI (including combined antimuscarinics and mirabegron)
  - Preexisting symptoms (dyspareunia / urgency symptoms)
- *Physical examination:*
  - Clinical tests :
    - Cough stress test
    - Cervico-urethral mobility (Marshall/Bonney Test, Ulmsten Test, Q Tip/cotton swab Test, other)
    - POP-Q:
      - If POP by grade and localization (anterior vaginal wall, apical, posterior vaginal wall)
      - POP associations
- *Nb of pads used/day (and by number of pads)*
- *Pad weight test (if done)*
- *Urodynamics testing (if done):*
  - maximum urine flow rate (+  $Q_{max} < 15$  ml)
  - post-void residual volume measurement (+ PVR > 150 ml)
  - Cystometry:
    - normal
    - bladder outlet obstruction,
    - detrusor over or underactivity,
    - urodynamic SUI
  - Measures of urethral pressure: (one of following methods)
    - MUCP
    - VLPP

- ALPP

- *Questionnaire ICIQ –UI-SF*

- Sum items 3+4+5
- Items 6

○ *Questionnaire I-QOL:*

- total scores and subscale scores: Avoidance and Limiting Behavior (ALB), Psychosocial Impacts (PS), and Social Embarrassment (SE).
- demographic questionnaire

○ *Questionnaire PISQ 12:*

- total scores
- Q5, Q6 and Q7 separately

3.2 Operative procedure:

- *Surgical Procedure :*

- Type of anesthesia
- Pre and intra-operative antibiotics
- Concomitant pelvic surgery (type): hysterectomy and/or surgical cure of a pelvic organ prolapse, association, other
- Blood loss
- Intra-op complications
- Duration
- Technical observations

- *Immediate post-operative data:*

- Post –operative antibiotics and duration
- Spontaneous post-op micturition or urinary drainage and duration
- Postoperative hospital stay/duration
- Post-void residual volume at discharge
- Maximum flow rate at discharge (if done)

3.3 follow up visits from first postoperative visit until 3 years after implantation:

○ *Incision healing* (first post-operative visit only)

○ *Local pain* (first post-operative visit only)

○ *Physical examination / interview patient:*

- Weight, BMI and change of BMI since baseline (excepted at first post-operative

- visit)
  - Urinary symptoms
  - Nb of pads used (question from the investigator to the patient).
  - Cough stress test
- Pad weight test (if done, according to current practice)
- *PVR and uroflowmetry (if available):*
  - post-void residual volume measurement
  - maximum urinary flow rate
- New Vaginal/Pelvic Intervention (confirmed by the investigator), excepted at first post-operative visit
- Questionnaire PGI-I
- Questionnaire ICIQ –Ui-SF
  - Sum items 3+4+5
  - Items 6
- Questionnaire I-QOL:
  - total scores and subscale scores
- Questionnaire PISQ -12:
  - total scores
  - Q5, Q6 and Q7
- Work stoppage: if yes, number of days (first follow-up visit only).
- Normal activity: number of days before returning to a normal activity (first follow-up visit only).
- Patient satisfaction
- Patient recommendation: recommend the surgery to a friend?

ICIQ-UI Short Form scoring: The ICIQ-UI Short Form is a questionnaire for evaluating the frequency, severity and impact on quality of life (QoL) of urinary incontinence in men and women in research and clinical practice across the world. Questions 3, 4 and 5 are summed to compute the total ICIQ SF score. This score may be divided into the following four severity categories: slight (1-5), moderate (6-12), severe (13-18) and very severe (19-21).

i-QOL scoring: The I-QOL produces quality-of-life profiles for people suffering from urinary incontinence. The survey consists of 22 items scored on a 5-point Likert scale providing a transformed summary score of 0 to 100 with higher scores indicating better quality of life. The 22 items can be further grouped into 3 subscales: Avoidance and Limiting Behavior (8 items), Psychosocial Impacts (9 items), and Social Embarrassment (5 items). The I-QOL and its subscale scores are computed by adding each item's response, subtracting the lowest possible score and dividing that sum by the possible raw score range. The scores are then transformed to have a range from 0 (maximum problem) to 100 (no problem at all). The formula used to compute the transformed score follows:

Scale score = (sum of items - lowest possible score) / possible raw score range \* 100

Missing data: if no more than three (of the 22) items are omitted, a mean substitution may be computed for these items. However it is recommended that i-QOL scores be set to missing if more than three items are left unanswered.

PISQ-12 scoring: the PISQ is a 12-item questionnaire with items selected through review of the literature, expert opinion and review of non-validated or generic questionnaires. Responses are graded on a 5-point Likert scale from 'never' to 'always'. The PISQ-12 is a validated and reliable short form that evaluates sexual function in heterosexual women with urinary incontinence and/or pelvic organ prolapsed and predicts long-form scores.

Scores are calculated by totaling the scores for each question with 0 = always, 4 = never. Reverse scoring is used for items 1, 2, 3 and 4. The short form questionnaire can be used with up to two missing responses. To handle missing values the sum is calculated by multiplying the number of items by the mean of the answered items. If there are more than two missing responses, the short form no longer accurately predicts long form scores. To make scores comparable to long form scores multiply the total by 2.58. Furthermore, questions 5, 6 and 7 can be evaluated separately.

The Patient Global Impression of Improvement (PGI-I) is a transition scale that is a single question asking to rate their urinary tract condition after treatment, as compared with how it was prior to before beginning treatment on a scale from 1 (very much better) to 7 (very much worse).

In case of discordances between the questionnaires and physician assessments, only questionnaires will be considered (number of pads used).

